6.5.5 Visit 05A, Day 15, Optional Leukapheresis

(Window: Day 15+4 weeks post study vaccination)

In addition to the study procedures listed in [Section 6.5](#), the following study procedures will also be performed:

- Subjects will be provided with a description of the Leukapheresis substudy (purpose and study procedures) and asked to read and sign the ICF prior to performing the procedure. A Leukapheresis specific informed consent may be needed prior to performing the procedure based on institutional requirements.
- Review eligibility criteria for leukapheresis procedure.
- Blood collection for safety labs required prior to the procedure.
- Urine or serum pregnancy test prior to the procedure.

- Only SAEs that occur during or within 24 hours after the leukapheresis study visit will be recorded on the appropriate DCF.

6.5.6 Visit 06, Day 29, Clinic Visit

(Window: Day 29±3 days post study vaccination)

In addition to the study procedures listed in [Section 6.5](#), the following study procedures will also be performed:

- Approximately 80 mL of venous blood will be collected for cellular immunology assays.
- Approximately 20 mL of venous blood will be collected for antibody assays.
- Approximately 32 mL of venous blood will be collected for PBMC and plasma storage for secondary research.
- All AEs/SAEs/AESIs including PIMMCs/MAAEs/NOCMCs will be recorded on the appropriate DCF.

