3.2 Study Objectives and Endpoints

Table 2: Objectives and Endpoints (Outcome Measures)

Objectives	Endpoints (Outcome Measures)
Primary	

 To assess the safety and tolerability of different doses of ChAd-S or ChAd-S-TCE, and SAM-S or SAM-S-TCE when administered as: 
 prime-boost in healthy naïve adult subjects boost in healthy adult subjects previously vaccinated with an EUA/licensed mRNA or adenoviral-vectorized COVID-19 vaccine 	
 Occurrence of solicited local reactogenicity signs and symptoms for 7 days following each study vaccination Occurrence of solicited systemic reactogenicity signs and symptoms for 7 days following each study vaccination Occurrence of unsolicited AEs for 28 days following each study vaccination Change from baseline for clinical safety laboratory parameters 7 days after each study vaccination Occurrence of SAEs and AESIs, including PIMMCs, MAAEs and NOCMCs, throughout the entire study following the first study vaccination
Secondary	

 To assess the humoral immunogenicity of ChAd-S or ChAd-S-TCE, and SAM-S or SAM-S-TCE 	
 Response rate, and magnitude of SARS-CoV-2-specific antibody binding and neutralization titers (including against emergent viral strains, e.g., B.1.1.7) in serum samples will be assessed via a range of assays measuring total Spike-specific IgG (ELISA-based), and function (neutralization, RBD binding, or similar) in serum on the following days:

Objectives	Endpoints (Outcome Measures)
	
For Stage 1, Groups 1 and 3A: Days 1 and 29 post Dose 1; then Days 29, 181, and 366 post Dose 2
 
For Stage 1, Groups 3B and 4: Days 1, 29, 57, and 85-130 post Dose 1; then Days 15, 29, 85, 181, and 366 post Dose 2
 
For Stage 2, Groups 5-7A*, 7B*, 9, 10A, 10B, and 11A, 11B, and 13-15: Days 1, 15, 29, 85, 181, and 366 post study vaccination
 
For Stage 2, Groups 8A*, 8B* and 12A, 12B: Days 1, 15, 29, and 57 post Dose 1; then Days 15, 29, 85, 181, and 366 post Dose 2

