6.2 Enrollment

6.2.1 Visit 01, Day 1, Clinic Visit, 1st Study Vaccination (Dose 1)

- Subject's willingness to participate will be reconfirmed and documented in the subject's study records prior to performing any further study procedures, including administration of the first study vaccination.
- Eligibility criteria, including results of the screening labs, will be reviewed with subjects prior to the first study vaccination to ensure eligibility. Subjects who have received approved COVID-19 booster vaccinations are no longer excluded. In addition, subjects with evidence of previous non-acute COVID-19 (serologically positive, but PCR negative) are also no longer excluded.
- Interim medical history, including an assessment for new medical conditions, stability of chronic diseases, will be obtained by interview of subjects prior to the first study

vaccination. Any changes in medical history since the screening visit will be reviewed with subjects prior to the first study vaccination to ensure continued eligibility.

- All concomitant medications (including solicitation for receipt of any non-study vaccines) will be reviewed with subjects prior to the first study vaccination for accuracy and completeness. Any new concomitant medications taken since the screening visit will be reviewed with subjects prior to the first study vaccination to ensure continued eligibility.
- Vital signs, including oral temperature, pulse, and BP, will be obtained prior to the first study vaccination to ensure continued eligibility. Vital signs assessed on Day 1 prior to the first study vaccination will be considered as baseline. Subjects must not eat or drink anything hot or cold within 10 minutes prior to taking oral temperature.
- A targeted physical examination may be performed prior to the first study vaccination, if indicated based on review of complete medical history and any updates obtained by interview of subjects since the screening visit, by a study clinician licensed to make medical diagnoses and listed on the Form FDA 1572 as the site PI or sub-investigator.
- A urine or serum pregnancy test will be performed locally by the site within 24 hours prior to the first study vaccination for all women of childbearing potential. Results must be negative and known prior to enrollment and the first study vaccination.
- A saliva sample will be collected to check for antibodies.

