6.5.7 Visit 07, Day 85, Clinic Visit

(Window: Day 85±3 days post study vaccination)

In addition to the study procedures listed in [Section 6.5](#), the following study procedures will also be performed:

- Approximately 80 mL of venous blood will be collected for cellular immunology assays.
- Approximately 20 mL of venous blood will be collected for antibody assays.
- Approximately 32 mL of venous blood will be collected for PBMC and plasma storage for secondary research.
- All SAEs/AESIs including PIMMCs/MAAEs/NOCMCs will be recorded on the appropriate DCF.

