6.6.12 Visit 12, Day 85, Clinic Visit

(Window: Day 29±3 days post 2nd study vaccination)

In addition to the study procedures listed in [Section 6.6](#), the following study procedures will also be performed:

- Approximately 72 mL of venous blood will be collected for cellular immunology assays.
- Approximately 20 mL of venous blood will be collected for antibody assays.
- Approximately 32 mL of venous blood will be collected for PBMC and plasma storage for secondary research.
- All AEs/SAEs/AESIs including PIMMCs/MAAEs/NOCMCs will be recorded on the appropriate DCF.

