6.8 Unscheduled Study Visits

An Unscheduled Visit may occur at any time during this trial and will be conducted in clinic or at home, based on participating site and subject preference. Any of the following activities may be performed:

- Interim medical history, including an assessment for new medical conditions will be obtained by interview of subjects and any changes since the previous clinic visit, phone call, or other form of contact will be noted (if indicated).
- All concomitant medications will be recorded on the appropriate DCF.

- All AEs will be recorded on the appropriate DCF (if prior to Visit 09 for Stage 1, Groups 1 and 3A, Visit 12 for Stage 1, Groups 3B and 4, Visit 06 for Stage 2, Groups 5-7A, 7B, 9, 10A, 10B, 11A, 11B, and 13-15, and Visit 12 for Stage 2, Groups 8A, 8B and 12A, 12B).
- Memory Aid information will be reviewed with subjects (if within 7 days after the last study vaccination).
- Vital signs, including oral temperature, pulse, and BP, may be obtained if indicated. Subjects must not eat or drink anything hot or cold within 10 minutes prior to taking oral temperature.
- A targeted physical examination may be performed, if indicated, based on review of interim medical history, by a study clinician licensed to make medical diagnoses and listed on the Form FDA 1572 as the site PI or sub-investigator.
- Approximately 14 mL of venous blood will be collected for clinical safety labs (WBC, HgB, PLT, ALT, AST, ALP, Cr, CK, and T Bili) will be performed by the central (clinical) laboratory (if indicated).
- If a participant presents with signs or symptoms suggestive of pericarditis or myocarditis within 6 weeks post vaccination, blood will be collected for troponin-I or troponin-T testing and an electrocardiogram (ECG) will be performed.
- Approximately 80 mL of venous blood will be collected for cellular immunology assays.
- Approximately 20 mL of venous blood will be collected for antibody assays.
- Approximately 32 mL of venous blood will be collected for PBMC and plasma storage for secondary research.
- STAGE 1, Groups 3B and 4 and STAGE 2, Groups 5, 6, 7A, 7B, 8A, 8B, 9, 10A, 10B, 11A, 11B, 12A, 12B, and 13-15: Approximately 2.5 mL of venous blood will be collected for identification of transcriptomal signatures associated with vaccine reactogenicity and immunogenicity (if on or prior to Day 8 of either vaccination).

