8.1.1.2 Unsolicited Adverse Events

Unsolicited non-serious AEs will be captured for 28 days following each study vaccination.

In addition, AESIs, including PIMMCs, MAAEs, and NOCMCs, will be captured throughout the entire study following the first study vaccination.

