Study Day post Study Vaccination	Scr -30 to -1d	D1	D2 +1d	D4 +2d	D8+2d	D15+2d	D15+4wk	D29 ±3d	D85 ±3d	D181 ±14d	D366 ±14d		
Blood Collection for PBMC and Plasma Storage		X				X		X	X	X	X	X	X
Blood Collection for Transcriptomal Signatures		X	X		X							X	X ⁵
Blood Collection for Cytokines		X	X		X							X	X
Enroll in Advantage eClinical		X											
Study Vaccination		X											
45 Minute Evaluation After Study Vaccination		X											
Distribute Memory Aid and Study Related Materials		X											
Review Memory Aid			X	X	X							X ⁵	X ⁵
Adverse Events		X	X	X	X	X		X				X ⁶	X ⁶
SAEs/AESIs including PIMMCs/MAAEs/NOCMCs		X	X	X	X	X	X ⁷	X	X	X	X	X	X
Optional Leukapheresis ⁸							X						
Saliva Collection for Antibodies		X			X								
Phone Call ⁹				X									

¹ Includes WBC, HgB, PLT, ALT, AST, ALP, T Bili, CK, Cr and PT/PTT

² Includes WBC, HgB, PLT, ALT, AST, ALP, T Bili, CK, and Cr, ³ Safety lab per local Leukapheresis procedure

⁴ If clinically indicated

⁵ If within 7 days after study vaccination

⁶ If prior to Study Visit 06

⁷ SAEs only

⁸ Extra screening visit may be needed prior to Leukapheresis procedure

⁹ Can be phone, text, or email contact

* After protocol version 9.0 was implemented, it was decided not to enroll subjects into Groups 7 and 8 because of competing priorities and predicted difficulties enrolling into these two groups.

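### Unsolicited AE collection has two different end points: 28 days after vaccination (Day 29) in the endpoint and safety sections, but a closing visit that may fall on Day 26 in the visit rules

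*Protocol*

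**What the plan says.** **Day-based statements.** Table 2 (Section 3.2) lists as a primary endpoint: "Occurrence of unsolicited AEs for 28 days following each study vaccination". Section 8.1.1.2 repeats the period: "Unsolicited non-serious AEs will be captured for 28 days following each study vaccination". Sections 8.2, 8.3 and 10.5 also use 28 days. Section 8.1 is looser and says approximately 28 days.

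**Visit-based statements.** In the single-boost groups, Visit 06 (Section 6.5.6) is the last scheduled visit at which all AEs are recorded, with "Window: Day 29±3 days post study vaccination". The next scheduled visit, Visit 07 on Day 85 (Section 6.5.7), has the narrower instruction "All SAEs/AESIs including PIMMCs/MAAEs/NOCMCs will be recorded on the appropriate DCF".

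For unscheduled visits, Section 6.8 begins its rule with "All AEs will be recorded on the appropriate DCF (if prior to Visit 09 for Stage 1, Groups 1 and 3A". It goes on to name Visit 12 for Groups 3B and 4, Visit 06 for the single-boost Stage 2 groups and Visit 12 for Groups 8 and 12. Section 6.7 applies the same rule to early termination. Footnote 6 of Table 8 reads "If prior to Study Visit 06", and Tables 6, 7 and 9 have matching footnotes for Visits 09 and 12.

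The closing visit after the second dose has the same tolerance, for example "Window: Day 29±3 days post 2nd study vaccination" in Section 6.6.12.

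**The concern.** The same collection period ends on a calendar day in one set of sections and at an appointment in another. The two agree only if the appointment falls on or after Day 29, and the window does not require that.

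If a site works from Sections 6.7 and 6.8 and the schedule, a subject seen on Day 26 has left non-serious AE collection while still inside the 28-day endpoint period. If it works from Section 8, the subject has not. Capture of a primary endpoint would then depend on the appointment date and on which section the site follows. An event never recorded cannot be restored at analysis. The DSMB review that Section 10.4.1 sets at the visit 28 days after the last vaccination would use the same data.

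The protocol avoids this for the solicited period: the visit that closes it is Day 8+2 (Section 6.5.3), a one-sided window that cannot open before the 7 days are complete.

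**Working it through.** **Inputs.**
- Endpoint length: 28 days (Table 2; Section 8.1.1.2).
- Day numbering: the vaccination day is Day 1, from the heading of Section 6.2.1, "Visit 01, Day 1, Clinic Visit, 1st Study Vaccination (Dose 1".
- Closing-visit window: Day 29±3, i.e. Days 26 to 32 (Section 6.5.6; likewise 6.3.7, 6.4.11 and 6.6.12 counted from the second dose).

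**Step 1, the plan's nominal figure.** Days elapsed = visit day − 1. At Day 29, 29 − 1 = 28, so the nominal visit matches the stated period exactly.

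**Step 2, early visits.** Days not covered = max(0, 28 − elapsed).

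| Closing visit | Elapsed | Not covered | Share of 28 |
|---|---|---|---|
| Day 26 | 25 | 3 | 10.7% |
| Day 27 | 26 | 2 | 7.1% |
| Day 28 | 27 | 1 | 3.6% |
| Days 29-32 | 28-31 | 0 | 0% |

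**Step 3, doses affected.** After the second dose, Visit 09 in Groups 1/3A and Visit 12 in Groups 3B/4 and 12 also have a floor of 25 elapsed days. First-dose periods in the two-dose groups are not shortened, because AE recording continues through the later visits.

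**Step 4, average loss (assumption).** The protocol does not say how visits spread over the window, so the mean loss can lie anywhere from 0 to 3 days. If visits were even over the seven days, it would be (3 + 2 + 1)/7 = 0.86 day, and 0.86/28 = 3.1% of the period.

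**Step 5, effect on detection (deliberately extreme assumptions).** Take a constant hazard over 28 days, every subject seen on Day 26, and no uncovered event captured by another route. With 28-day rate p, the observed rate is q = 1 − (1 − p)^(25/28), and the chance of at least one event in n subjects is 1 − (1 − q)^n. For n = 10, full coverage reproduces the Table 4 figures:

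| p | Full coverage (Table 4) | All seen on Day 26 |
|---|---|---|
| 20% | 89.3% | 86.4% |
| 10% | 65.1% | 61.0% |
| 4% | 33.5% | 30.5% |

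**Step 6, other routes of capture.** The Memory Aid runs only from Day 1 through Day 8 (Section 7.1), and the optional leukapheresis visit records SAEs only (Section 6.5.5). SAEs, AESIs, PIMMCs, MAAEs and NOCMCs are recorded to study end. At Day 85 the interim history looks back to the previous contact (Section 6.5), but that visit has no instruction to record other AEs.

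**The case against.** The best defence is that Section 8 governs safety collection and is day-based throughout. Section 8.4 also makes the investigator responsible for recording every AE observed or reported in the trial. On that view the visit lists only say what is done at each visit and cancel nothing. Section 8.1's looser wording also suits a nominal Day 29±3 visit. This stands far enough to rule out a stronger reading: a reader might infer that the protocol prescribes the loss of these days. It does not; it contradicts itself, and the days may or may not be collected.

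A reader might also infer that a subject returning to the clinic on Day 28, after a Day 26 visit, would have the event left out. Section 8.1.5 defines an MAAE broadly enough to include any unscheduled visit to medical personnel, and MAAEs are recorded at unscheduled visits without a visit limit. That return would arguably be captured.

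A third tempting inference is that AE rates in Group 12 would rest on a continuous period of about 84 days. The schedule does collect AEs between the two doses, but collecting more loses nothing, and the endpoint is still 28 days after each dose. Tabulation by onset date belongs to the SAP.

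Finally, the study is descriptive, groups have at most 12 subjects, and no between-group testing is planned (Section 10.1), so the practical effect is small. That is correct. It limits the size of the point but does not reconcile the two end points.

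**Conclusion.** The inconsistency is real and minor. The endpoint and Section 8 end collection on Day 29; Sections 6.7 and 6.8 and the schedule footnotes end it at a visit that may fall on Day 26. If the visit-based rule is followed, up to 3 of 28 days (10.7%) after the last dose may go uncollected. The even-spread assumption gives 3.1% on average.

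The exposed events are narrow: non-serious AEs, not medically attended, not AESIs or NOCMCs, with onset between an early closing visit and Day 29. Solicited reactions, Day 8 laboratory data, SAEs and AESIs are untouched. Any loss goes one way, toward fewer AEs. Even under the extreme assumptions above, detection in a group of 10 falls by about 3 to 4 percentage points. Nothing here threatens the trial's conclusions; it is worth correcting because the correction is cheap and the endpoint is primary.

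**What to change.** For groups still in follow-up:

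1. In Sections 6.7 and 6.8 and the matching schedule footnotes, replace the cut-off at Visit 06, 09 or 12 with onset on or before Day 29 after a study vaccination, so that they agree with Table 2 and Section 8.
2. For any subject whose closing visit falls on Days 26-28, add one phone, text or email contact on or after Day 29 to complete AE recording.
3. Leave the ±3-day window in place for the immunogenicity draw.

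This brings the uncovered time to 0 of 28 days whatever the visit date. The cost is a wording change and one short remote contact for the subjects seen early; the protocol already uses that contact mode on Day 4. Groups 7 and 8 will not be opened, and Stage 1 enrolled before version 5.0, so in practice the change matters only for subjects who have not yet passed Day 29 after their last dose.

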6.5.7 Visit 07, Day 85, Clinic Visit

(Window: Day 85±3 days post study vaccination)

In addition to the study procedures listed in [Section 6.5](#), the following study procedures will also be performed:

- Approximately 80 mL of venous blood will be collected for cellular immunology assays.
- Approximately 20 mL of venous blood will be collected for antibody assays.
- Approximately 32 mL of venous blood will be collected for PBMC and plasma storage for secondary research.
- All SAEs/AESIs including PIMMCs/MAAEs/NOCMCs will be recorded on the appropriate DCF.

6.5.8 Visit 08, Day 181, Clinic Visit

(Window: Day 181±14 days post study vaccination)

In addition to the study procedures listed in [Section 6.5](#), the following study procedures will also be performed:

- Approximately 80 mL of venous blood will be collected for cellular immunology assays.

- Approximately 20 mL of venous blood will be collected for antibody assays.
- Approximately 32 mL of venous blood will be collected for PBMC and plasma storage for secondary research.
- All SAEs/AESIs including PIMMCs/MAAEs/NOCMCs will be recorded on the appropriate DCF.

6.5.9 Visit 09, Day 366, Clinic Visit, Final Study Visit

(Window: Day 366±14 days post study vaccination)

In addition to the study procedures listed in [Section 6.5](#), the following study procedures will also be performed:

- Approximately 80 mL of venous blood will be collected for cellular immunology assays.
- Approximately 20 mL of venous blood will be collected for antibody assays.
- Approximately 32 mL of venous blood will be collected for PBMC and plasma storage for secondary research.
- All SAEs/AESIs including PIMMCs/MAAEs/NOCMCs will be recorded on the appropriate DCF.

6.6 Planned Study Visits for Groups 8A, 8B and 12A, 12B

At all clinic visits for Groups 8A, 8B, and 12A, 12B, the following study procedures will be performed:

- Interim medical history, including an assessment for new medical conditions, stability of chronic diseases will be obtained by interview of subjects and any changes since the previous clinic visit, phone call or other form of contact will be noted.
- All concomitant medications will be recorded on the appropriate DCF.
- Vital signs, including oral temperature, pulse, and BP, will be obtained. Subjects must not eat or drink anything hot or cold within 10 minutes prior to taking oral temperature.
- A targeted physical examination may be performed, if indicated, based on review of interim medical history, by a study clinician licensed to make medical diagnoses and listed on the Form FDA 1572 as the site PI or sub-investigator.

6.6.1 Visit 02, Day 2, Clinic Visit,**(Window: Day 2+1 day 1st post study vaccination)**

In addition to the study procedures listed in [Section 6.6](#), the following study procedures will also be performed:

- Memory Aid information will be reviewed with subjects.
- Approximately 2.5 mL of venous blood will be collected for identification of transcriptomal signatures associated with vaccine reactogenicity and immunogenicity.
- Approximately 4 mL of blood will be collected for cytokines.
- All AEs/SAEs/AESIs including PIMMCs/MAAEs/NOCMCs will be recorded on the appropriate DCF.

6.6.2 Visit 03, Day 4, Telephone, Email, or Text Contact**(Window: Day 4+2 days post 1st study vaccination)**

- Memory Aids will be reviewed with the subjects via telephone, email, or text for any AEs (solicited injection site and systemic reactions, as well as unsolicited AEs), SAEs, AESIs, and concomitant medications. Based on the information collected, subjects may be asked to return to the clinic for an evaluation.

6.6.3 Visit 04, Day 8, Clinic Visit**(Window: Day 8+2 days post 1st study vaccination)**

In addition to the study procedures listed in [Section 6.6](#), the following study procedures will also be performed:

- Memory Aid information will be reviewed with subjects.
- A saliva sample will be collected to check for antibodies.
- Approximately 14 mL of venous blood will be collected for safety labs including WBC, HgB, PLT, ALT, AST, ALP, Cr, CK and T Bili.
- Approximately 2.5 mL of venous blood will be collected for identification of transcriptomal signatures associated with vaccine reactogenicity and immunogenicity.
- Approximately 4 mL of blood will be collected for cytokines.

- All AEs/SAEs/AESIs including PIMMCs/MAAEs/NOCMCs will be recorded on the appropriate DCF.

6.6.4 Visit 05, Day 15, Clinic Visit

(Window: Day 15+2 days post 1st study vaccination)

In addition to the study procedures listed in [Section 6.6](#), the following study procedures will also be performed:

- Approximately 72 mL of venous blood will be collected for cellular immunology assays.
- Approximately 20 mL of venous blood will be collected for antibody assays.
- Approximately 24 mL of venous blood will be collected for PBMC and plasma storage for secondary research.
- All AEs/SAEs/AESIs including PIMMCs/MAAEs/NOCMCs will be recorded on the appropriate DCF.

